5.4 General Concomitant Medication and Supportive Care Guidelines

There are no known potential interactions between SBRT and concomitant medications.

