8. STUDY CALENDAR

Note that the study calendar is based on the ideal subject. The schedule should be followed as closely as realistically possible, but may be modified due to problems such as scheduling delays, conflicts such as clinic closure or poor weather conditions, or other unforeseeable events.

	Pre-Study ¹	SBRT ^{3,9}	Follow-up (in time Post-RT)									
			4 weeks (± 7 days)	3 mo ⁶	6 mo ⁶	9 mo ⁶	12 mo ⁶	18 mo ⁷	24 mo ⁷	30 mo ⁷	36 mo ⁷	
Informed Consent	X											
Demographics	X											Follow for survival
Medical History	X											
Physical Exam	X		X	X	X	X	X	X	X	X	X	
Height	X											
Weight & Vitals	X	X	X	X	X	X	X	X	X	X	X	
Performance Status	X	X	X	X	X	X	X	X	X	X	X	
Biopsy-confirmed sarcoma	X											
Treatment planning scan	X											
CBC w/ diff, plts, CMP	X ₄		X	X	X	X	X	X	X	X	X	
CT of treatment site	X ₈			X	X	X	X	X	X	X	X	
MRI	X ₅			X ₁₁	X ₁₁	X ₁₁	X ₁₁	X ₁₁	X ₁₁	X ₁₁	X ₁₁	
FDG-PET (optional)	X			X ₁₁	X ₁₁	X ₁₁	X ₁₁	X ₁₁	X ₁₁	X ₁₁	X ₁₁	
Tumor measurements	X			X	X	X	X	X	X	X	X	
Pregnancy test ²	X											
Pain Assessments ¹⁰	X	X	X	X	X	X	X	X	X	X	X	
Toxicity Assessment		X	X	X	X	X	X	X	X	X	X	

¹Pre-SBRT assessments should be performed within 4 weeks of radiation treatment

²Pregnancy test by urine or serum, for women who are not post-menopausal as defined in Appendix A

³ Patients will receive SBRT over a five-day period. Ideally all 5 fractions should be delivered Monday through Friday, however it may be delivered over two weeks
⁴ Within 1 week prior to radiotherapy
⁵ Optional depending on treatment site
⁶ Follow-up should occur +/- 14 days
⁷ Follow-up should occur +/- 30 days
⁸ CT scan must be performed within 4 weeks prior to the start of therapy, not required if MRI is obtained.
⁹ Patients will be able to receive chemotherapy 2 weeks after the completion of SBRT.
¹⁰ Brief Pain Inventory (Appendix C) and 10 point Visual Analog Scale (Appendix F); given the age population, the completion of these assessments may not be possible and therefore are optional for subjects under 18 years of age
¹¹ Follow-up PET/CT and MRI are at the discretion of the treating physician and are optional

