- Quality of life will be assessed using the Brief Pain Inventory form and 10 point Visual Analog Scale. An overall score will be calculated pre-treatment and at the time of the 2nd radiologic reassessment. The change in score will be evaluated with a Wilcoxon signed-rank test.

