APPENDIX C Brief Pain Inventory Form

STUDY ID# _____

HOSPITAL # _____

DO NOT WRITE ABOVE THIS LINE

Brief Pain Inventory (Short Form)

Date: ____ / ____ / ____

Time: ____

Name: _____

Last

First

[figure not shown]
Middle Initial

1. Throughout our lives, most of us have had pain from time to time (such as minor headaches, sprains, and toothaches). Have you had pain other than these everyday kinds of pain today?

1. Yes

2. No

2. On the diagram, shade in the areas where you feel pain. Put an X on the area that hurts the most.

3. Please rate your pain by circling the one number that best describes your pain at its **worst** in the last 24 hours.

4. Please rate your pain by circling the one number that best describes your pain at its **least** in the last 24 hours.

5. Please rate your pain by circling the one number that best describes your pain on the **average**.

6. Please rate your pain by circling the one number that tells how much pain you have **right now**.

7. What treatments or medications are you receiving for your pain?

8. In the last 24 hours, how much relief have pain treatments or medications provided? Please circle the one percentage that most shows how much relief you have received.

0% 10% 20% 30% 40% 50% 60% 70% 80% 90% 100%
No Complete
Relief Relief

9. Circle the one number that describes how, during the past 24 hours, pain has interfered with your:

A. General Activity

0 1 2 3 4 5 6 7 8 9 10
Does not Completely
Interfere Interferes

B. Mood

0 1 2 3 4 5 6 7 8 9 10
Does not Completely
Interfere Interferes

C. Walking Ability

0 1 2 3 4 5 6 7 8 9 10
Does not Completely
Interfere Interferes

D. Normal Work (includes both work outside the home and housework)

0 1 2 3 4 5 6 7 8 9 10
Does not Completely
Interfere Interferes

E. Relations with other people

0 1 2 3 4 5 6 7 8 9 10
Does not Completely
Interfere Interferes

F. Sleep

0 1 2 3 4 5 6 7 8 9 10
Does not Completely
Interfere Interferes

G. Enjoyment of life

0 1 2 3 4 5 6 7 8 9 10
Does not Completely
Interfere Interferes

Copyright 1991 [name]
Pain Research Group
All rights reserved.

Used by permission.

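### The before-after pain score is tested without regard to analgesic use, which the Brief Pain Inventory already asks about, so a score change cannot be told apart from an analgesic change in either direction

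*Combined protocol and SAP*

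**What the plan says.** Objective 1.2.4 compares patient-completed pain forms before and after SBRT. Section 13.3.2 gives the whole analysis in three sentences. The instruments: "Quality of life will be assessed using the Brief Pain Inventory form and 10 point Visual Analog Scale". The quantity and its timing: "An overall score will be calculated pre-treatment and at the time of the 2nd radiologic reassessment". The test: "The change in score will be evaluated with a Wilcoxon signed-rank test". The trial has one arm (Protocol Summary).

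The form in Appendix C goes beyond pain ratings. Item 7 is an open question: "What treatments or medications are you receiving for your pain". Item 8 asks, on a percentage scale, "In the last 24 hours, how much relief have pain treatments or medications provided". The pain-assessment row of the Section 8 calendar schedules this form before treatment, at SBRT and at every follow-up visit, although footnote 10 says the pain assessments "therefore are optional for subjects under 18 years of age".

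On concomitant medication, Section 5.4 says only: "There are no known potential interactions between SBRT and concomitant medications". Footnote 9 of the calendar adds: "Patients will be able to receive chemotherapy 2 weeks after the completion of SBRT".

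**The concern.** Pain scores respond directly to analgesics. A patient whose rating falls because pain medication was started or raised counts as improved under the planned test. A patient whose rating is unchanged after pain medication was stopped counts as no change. No comparator arm experiences the same analgesic changes, so nothing in the analysis offsets them.

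What is at stake is how far the pain result can be interpreted. Objective 1.2.4 could show a significant change that reflects prescribing, or miss a real improvement that appears as less medication. The plan asks patients for the information that would help a reader judge this and then leaves it out of the analysis.

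**Working it through.** **Step 1: does any other section close the gap?**

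| Place | What it contributes |
|---|---|
| 13.3.2, quality of life | Paired score change and signed-rank test; no covariate, stratification, composite or sensitivity analysis |
| 13.3.2, Cox models | Key covariates apply to OS, PFS, TTP and locoregional control only |
| 5.4 | One sentence on interactions; nothing on recording or analysing analgesics |
| 8, calendar | No medication row; analgesic use reaches the data only through items 7 and 8 of the pain form |
| 10.1, form schedule | No concomitant-medication form |
| 7.3 | Toxicity below grade 3 stays off the adverse event log and case report forms |
| Appendix C, items 7 and 8 | Analgesic use and relief are requested, with no stated use |

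None of these closes it. Item 7 is free text, so it cannot be part of a numeric total. The overall score is undefined, so whether item 8 enters it is unknown.

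**Step 2: is there a figure in the plan to reproduce?** No. The documents give no alpha, SD, effect size or expected number of pairs for this test. The only bound is 20 pairs, the enrolment goal in 13.2; fewer are likely because the forms are optional under 18. What follows is an illustration on assumed inputs.

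**Step 3: one-way escalation with no true effect.** Each patient's change is drawn as N(0, SD) - d × E. E is 1 with probability f (analgesics escalated) and 0 otherwise, and d is the points gained. Assumed: 15 pairs, SD 2.5, two-sided 5%. The mean shift due to analgesics alone is f × d. The standard error of a mean change without escalation is 2.5/√15 = 0.65.

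| f | d | Mean shift f × d | Trials with significant improvement |
|---|---|---|---|
| 0 | n/a | 0 | about 2-3% |
| 0.30 | 2 | 0.6 | about 11% |
| 0.30 | 3 | 0.9 | about 19% |
| 0.50 | 2 | 1.0 | about 25% |
| 0.50 | 3 | 1.5 | about 43% |

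With f = 0.50 and d = 2 to 3, the range is about 18-29% for 10 pairs and 33-56% for 20 pairs.

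**Step 4: escalation and reduction in equal shares.** Let f/2 of patients escalate and f/2 reduce, with the same d. The mean shift is (f/2) × d - (f/2) × d = 0. For f = 0.30 or 0.50 and d = 2 or 3, the rate of significant improvement stays at about 2-3%.

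**Step 5: the opposite error.** Suppose a true 2-point benefit with 15 pairs and SD 2.5. With no analgesic change the test succeeds in about 80% of trials. If a share f reduce analgesics and lose those 2 points, the mean benefit is 2 - 2f: 1.4 points at f = 0.30 and 1.0 at f = 0.50. The success rate falls to about 46% and 25%.

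**The case against.** The strongest reply is that the plan asks a descriptive question. Objective 1.2.4 and Section 13.3.1 speak of quality of life following SBRT, and pain under whatever care is given is a coherent target. If scores fall, rejecting no change in score is correct. This stands. A reader might infer that the plan will report analgesic escalation as benefit from SBRT, but no section makes that attribution. The weaker point survives: with SBRT the only study treatment, a significant change is likely to be read that way, and the analysis offers nothing to check it.

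Second, accounting for analgesics would not isolate SBRT. Chemotherapy is allowed from 2 weeks after SBRT. The calendar's first follow-up CT is at 3 months, so the second reassessment comes later than that; even if the 4-week response evaluation in Section 9.1 were counted as the first, the second would be at 3 months. Either way chemotherapy falls inside the window. This stands, and it limits what the fix may claim.

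Third, the simulation lets analgesics move one way and rests on assumed inputs. It is tempting to read 11-43% as the test's expected false-positive rate. Step 4 shows why that is unsupported: balanced changes give about 2-3%. Section 5.7 also moves patients who progress to survival-only follow-up, so pairs at the analysed visit would come mainly from progression-free patients. Escalation driven by progression is probably under-represented among them; this is an inference from the follow-up rule.

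Fourth, a simple responder rule (lower worst pain without more analgesics) would be faulty. Pain is not an eligibility criterion in Section 3, so a patient with no baseline pain could never respond, and one who stops analgesics with unchanged pain would count as a failure. This stands and shapes the fix.

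**Conclusion.** The gap is real and minor. Section 13.3.2 gives the analgesic information on the Brief Pain Inventory no role, and no other section supplies one, so a change in score cannot be told apart from a change in analgesics, in either direction. This conclusion rests on the text alone.

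The size is illustrative. It depends on an assumed SD, number of pairs, escalation share, points gained and alpha, none of which the documents give. It also depends on direction: Step 3 applies only if escalation dominates, and Step 5 only if reduction does.

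It would also be wrong to infer that analgesic use goes unrecorded: the form requests it at each scheduled pain assessment. What is missing is dose in codable form and any use in the analysis. Local control, the sample size and the safety rule are untouched.

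**What to change.** In Section 13.3.2:

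1. Record analgesic name and daily dose beside item 7, and code each patient at the analysed visit, relative to baseline, as analgesics increased, unchanged or decreased. State beforehand what counts as a change.
2. Keep the signed-rank test and report the score change by that category.
3. Add a supportive pain-response proportion with an exact interval, among patients with baseline worst pain above 0 or on analgesics at baseline. Response is reduced worst pain without an analgesic increase, or reduced analgesics without worse pain. Patients whose analgesics increased are non-responders.
4. State that the result describes pain after SBRT under concurrent care, including chemotherapy, and does not isolate an SBRT effect.

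The change of classification is as follows:

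| Pattern | Raw score change | Pain-response proportion |
|---|---|---|
| Worst pain lower, analgesics increased | Improved | Non-responder |
| Worst pain lower, analgesics unchanged | Improved | Responder |
| Worst pain unchanged, analgesics decreased | No change | Responder |
| No baseline pain and no baseline analgesics | Cannot improve | Not in denominator |

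These are recording and analysis definitions; they place no restriction on prescribing. The cost is one coded field and one table, with no change in sample size. The interval will be wide because the forms are optional under 18, and the pain result may look less favourable. Dose is hard to reconstruct from free text, so the coding should be set before data collection or, at the latest, before analysis.

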13.4 Reporting and Exclusions

13.4.1 Evaluation of toxicity. All patients will be evaluable for toxicity from the time of their first treatment with SBRT.

13.4.2 Evaluation of response. All patients included in the study must be assessed for response to treatment, even if there are major protocol treatment deviations. Each patient will be assigned one of the following categories: 1) complete response, 2) stable disease, 3) progressive disease, 4) early death from malignant disease (defined as death prior to first evaluation after completion of SBRT), 5) early death from toxicity, 6) early death because of other cause, or 9) unknown (not assessable, insufficient data). [Note: By arbitrary convention, category 9 usually designates the “unknown” status of any type of data in a clinical database.]

All of the patients who were enrolled on the trial should be included in the main analysis of local control.

All conclusions should be based on all enrolled subjects. Sub-analyses may then be performed on the basis of a subset of patients, excluding those for whom major protocol deviations have been identified (e.g., early death due to other reasons, early discontinuation of treatment, major protocol violations, etc.). However, these sub-analyses may not serve as the basis for drawing conclusions concerning treatment efficacy, and the reasons for excluding patients from the analysis should be clearly reported. The reason for performing subset analyses would be to generate hypotheses for future prospective clinical trials.

Appendix A

Definition of Menopausal Status:

Menopausal status will be defined according to the following criteria:

Post-menopausal:

- Woman 60 years of age or older
- Woman aged 45-59 years with spontaneous cessation of menses for at least 12 months prior to registration
- Woman aged 45-59 years with cessation of menses for less than 12 months prior to registration AND an FSH level in the postmenopausal range (or >34.4 IU/L if institutional range is not available)
- Woman aged 45-59 years on hormone replacement therapy who have discontinued hormone replacement therapy at diagnosis of breast carcinoma and have an FSH level in the postmenopausal range according to institutional/laboratory standards (or 34.4 IU/L if the institutional range is not available)
- Prior bilateral oophorectomy
- Woman younger than 60 years of age who have had a prior hysterectomy (without bilateral oophorectomy) AND who have an FSH level in the postmenopausal range (or >34.4 IU/L if institutional range is not available)

Pre- or peri-menopausal: Not meeting definition for postmenopausal as outlined above.

APPENDIX B

Dose Fractionation Schedule				
Dose Level	Dose/Fraction (cGy)	Fractions	Total Dose (cGy)	Biologic Equivalent Dose* (BED₄) cGy
Standard Dose for Palliation	300	10	3000	5250
Standard Dose for Definitive RT	180	28-30	50405400	7308-7830
Study Dose	800	5	4000	12000

 Biologically Equivalent Dose (BED) Calculation

APPENDIX C Brief Pain Inventory Form

STUDY ID# _____

HOSPITAL # _____

DO NOT WRITE ABOVE THIS LINE

Brief Pain Inventory (Short Form)

Date: ____ / ____ / ____

Time: ____

Name: _____

Last

First

[figure not shown]
Middle Initial

1. Throughout our lives, most of us have had pain from time to time (such as minor headaches, sprains, and toothaches). Have you had pain other than these everyday kinds of pain today?

1. Yes

2. No

2. On the diagram, shade in the areas where you feel pain. Put an X on the area that hurts the most.

3. Please rate your pain by circling the one number that best describes your pain at its **worst** in the last 24 hours.

4. Please rate your pain by circling the one number that best describes your pain at its **least** in the last 24 hours.

5. Please rate your pain by circling the one number that best describes your pain on the **average**.

6. Please rate your pain by circling the one number that tells how much pain you have **right now**.

7. What treatments or medications are you receiving for your pain?

8. In the last 24 hours, how much relief have pain treatments or medications provided? Please circle the one percentage that most shows how much relief you have received.

0% 10% 20% 30% 40% 50% 60% 70% 80% 90% 100%
No Complete
Relief Relief

9. Circle the one number that describes how, during the past 24 hours, pain has interfered with your:

A. General Activity

0 1 2 3 4 5 6 7 8 9 10
Does not Completely
Interfere Interferes

B. Mood

0 1 2 3 4 5 6 7 8 9 10
Does not Completely
Interfere Interferes

C. Walking Ability

0 1 2 3 4 5 6 7 8 9 10
Does not Completely
Interfere Interferes

D. Normal Work (includes both work outside the home and housework)

0 1 2 3 4 5 6 7 8 9 10
Does not Completely
Interfere Interferes

E. Relations with other people

0 1 2 3 4 5 6 7 8 9 10
Does not Completely
Interfere Interferes

F. Sleep

0 1 2 3 4 5 6 7 8 9 10
Does not Completely
Interfere Interferes

G. Enjoyment of life

0 1 2 3 4 5 6 7 8 9 10
Does not Completely
Interfere Interferes

Copyright 1991 [name]
Pain Research Group
All rights reserved.

Used by permission.

APPENDIX D DOSE CONSTRAINTS

Dose Constraints for Five Fractions – Based upon the AAPM Report TG 101³² reduced by 10% based on the assumption that patients on protocol have received prior systemic chemotherapy.

Serial Tissue	Volume	Volume Max (Gy)	Max Point Dose (Gy)	Endpoint (\geq Grade 3)
Optic Pathway	<0.2 cc	18 Gy (3.6 Gy/fx)	22.5 Gy (4.5 Gy/fx)	neuritis
Cochlea			24.7 Gy (4.95 Gy/fx)	hearing loss
Brainstem	<1 cc	23.4 Gy (4.68 Gy/fx)	31 Gy (6.2 Gy/fx)	cranial neuropathy
Spinal Cord	<0.25 cc	20.2 Gy (4.05 Gy/fx)	27 Gy (5.4 Gy/fx)	myelitis
	<1.2 cc	12.1 Gy (2.43 Gy/fx)		
Thecal Sac	<2.5 cc	20.2 Gy (4.05 Gy/fx)	30 Gy (6 Gy/fx)	myelitis
	<5 cc	15 Gy (3 Gy/fx)		
Cauda Equina	<5 cc	27 Gy (5.4 Gy/fx)	28.8 Gy (5.76 Gy/fx)	neuritis
Sacral Plexus	<3 cc	27 Gy (5.4 Gy/fx)	28.8 Gy (5.76 Gy/fx)	neuropathy
Rib	<1 cc	31.5 Gy (6.3 Gy/fx)	38.7 Gy (7.74 Gy/fx)	Pain or fracture
Esophagus*	<5 cc	24.7 Gy (4.95 Gy/fx)	31.5 Gy (6.3 Gy/fx)	stenosis/fistula
Ipsilateral Brachial Plexus	<3 cc	27 Gy (5.4 Gy/fx)	28.8 Gy (5.76 Gy/fx)	neuropathy
Heart/Pericardium	<15 cc	28.8 Gy (5.76 Gy/fx)	34.2 Gy (6.84 Gy/fx)	pericarditis
Great vessels	<10 cc	42.3 Gy (8.46 Gy/fx)	47.7 Gy (9.54 Gy/fx)	aneurysm
Trachea and Ipsilateral Bronchus*	<4 cc	16.2 Gy (3.24 Gy/fx)	34.2 Gy (6.84 Gy/fx)	stenosis/fistula
Skin	<10 cc	27 Gy (5.4 Gy/fx)	28.8 Gy (5.76 Gy/fx)	ulceration
Stomach	<10 cc	25.2 Gy (5.04 Gy/fx)	28.8 Gy (5.76 Gy/fx)	ulceration/fistula
Duodenum*	<5 cc	16.2 Gy (3.24 Gy/fx)	28.8 Gy (5.76 Gy/fx)	ulceration
Jejunum/Ileum*	<5 cc	17.5 Gy (3.51 Gy/fx)	31.5 Gy (6.3 Gy/fx)	enteritis/obstruction
Colon*	<20cc	22.5 Gy (4.5 Gy/fx)	34.2 Gy (6.84 Gy/fx)	colitis/fistula
Rectum*	<20cc	22.5 Gy (4.5 Gy/fx)	34.2 Gy (6.84 Gy/fx)	proctitis/fistula
Bladder wall	<15 cc	16.4 Gy (3.28 Gy/fx)	34.2 Gy (6.84 Gy/fx)	cystitis/fistula
Penile Bulb	<3 cc	27 Gy (5.4 Gy/fx)	45 Gy (9 Gy/fx)	impotence
Femoral Heads (Right & Left)	<10 cc	27 Gy (5.4 Gy/fx)		necrosis
Renal hilum/vascular trunk	<2/3 volume	20.7 Gy (4.14 Gy/fx)		malignant hypertension
Parallel Tissue	Volume	Critical Volume Dose		Endpoint (\geq Grade 3)
Lung (Right & Left)	1500 cc	11.2 Gy (2.25 Gy/fx)		Basic Lung Function
Lung (Right & Left)	1000 cc	12.1 Gy (2.4 Gy/fx)		Pneumonitis
Liver	700 cc	18.9 Gy (3.78 Gy/fx)		Basic Liver Function
Renal cortex (Right & Left)	200 cc	15.7 Gy (3.15 Gy/fx)		Basic renal function

*Avoid circumferential irradiation

Guidelines for Spillage

High Dose Spillage:

1. Any dose > 105% of the prescription dose should occur primarily within the PTV itself and not within the normal tissues outside the PTV. Therefore, the cumulative volume of all tissue outside the PTV receiving a dose > 105% of prescription dose should not be more than 15% of the PTV volume.
2. Conformality of PTV coverage will be judged such that the ratio of the volume of the prescription isodose meeting criteria 1 through 4 to the volume of the PTV is ideally < 1.2 (see table below). These criteria will not be required to be met in treating very small tumors (< 2.5 cm axial GTV dimension or < 1.5 cm craniocaudal GTV dimension) in which the required minimum field size of 3.5 cm results in the inability to meet a conformality ratio of 1.2.

Low Dose Spillage

1. The falloff gradient beyond the PTV extending into normal tissue structures must be rapid in all directions and meet the following criteria:
 - a. The maximum total dose over all fractions in Gray (Gy) to any point 2 cm or greater away from the PTV in any direction must be no greater than D2cm where D2cm is given by the table below.
2. The ratio of the volume of 50% of the prescription dose isodose to the volume of the PTV must be no greater than R50% where R50% is given. See Table below.
3. Respect all critical organ dose-volume limits listed above

Table 1: Conformality of Prescribed Dose for Calculations Based on Deposition of Photon Beam Energy in Heterogeneous Tissue

PTV Volume (cc)	Ratio of Prescription Isodose Volume to the PTV volume		Ratio of 50% Prescription Isodose Volume to the PTV Volume, R50%		Maximum dose (in% of dose prescribed) @ 2 cm from PTV in Any Direction, D2cm (Gy)		Percent of Lung Receiving 20 Gy Total or More, V20 (%)	
1.8	<1.2	<1.5	<5.9	<7.5	<50.0	<57.0	<10	<15
3.8	<1.2	<1.5	<5.5	<6.5	<50.0	<57.0	<10	<15
7.4	<1.2	<1.5	<5.1	<6.0	<50.0	<58.0	<10	<15
13.2	<1.2	<1.5	<4.7	<5.8	<50.0	<58.0	<10	<15
22.0	<1.2	<1.5	<4.5	<5.5	<54.0	<63.0	<10	<15
34.0	<1.2	<1.5	<4.3	<5.3	<58.0	<68.0	<10	<15
50.0	<1.2	<1.5	<4.0	<5.0	<62.0	<77.0	<10	<15
70.0	<1.2	<1.5	<3.5	<4.8	<66.0	<86.0	<10	<15
95.0	<1.2	<1.5	<3.3	<4.4	<70.0	<89.0	<10	<15
126.0	<1.2	<1.5	<3.1	<4.0	<73.0	>91.0	<10	<15

163.0	<1.2	<1.5	<2.9	<3.7	<77.0	>94.0	<10	<15
-------	------	------	------	------	-------	-------	-----	-----

APPENDIX E Performance Status Criteria – Lansky Performance Scale

ECOG Performance Status Scale		Karnofsky Performance Scale	
Grade	Descriptions	Percent	Description
0	Normal activity. Fully active, able to carry on all pre-disease performance without restriction.	100	Normal, no complaints, no evidence of disease.
		90	Able to carry on normal activity; minor signs or symptoms of disease.
1	Symptoms, but ambulatory. Restricted in physically strenuous activity, but ambulatory and able to carry out work of a light or sedentary nature (e.g., light housework, office work).	80	Normal activity with effort; some signs or symptoms of disease.
		70	Cares for self, unable to carry on normal activity or to do active work.
2	In bed <50% of the time. Ambulatory and capable of all self-care, but unable to carry out any work activities. Up and about more than 50% of waking hours.	60	Requires occasional assistance, but is able to care for most of his/her needs.
		50	Requires considerable assistance and frequent medical care.
3	In bed >50% of the time. Capable of only limited self-care, confined to bed or chair more than 50% of waking hours.	40	Disabled, requires special care and assistance.
		30	Severely disabled, hospitalization indicated. Death not imminent.

4	100% bedridden. Completely disabled. Cannot carry on any self-care. Totally confined to bed or chair.	20	Very sick, hospitalization indicated. Death not imminent.
		10	Moribund, fatal processes progressing rapidly.
5	Dead.	0	Dead.

